6.6. Biomarkers

Blood samples to assess biomarkers of CV disease and response will be taken in all subjects enrolled in the study, at the times specified in [Table 1](#). Biomarker samples will be stored by GSK and/or TIMI or one of their appointed designees. Additional description of the CV biomarkers is in [Appendix 5](#) and the assessments are considered exploratory.

Blood samples to assess hsCRP will be obtained from all subjects in Part A at designated time points ([Table 1](#)). In addition, in an expanded laboratory substudy in Part A, blood samples will be obtained in a subset of 600 subjects to assess NTproBNP and hsCRP ([Table 2](#), [Appendix 5](#)). Enrollment in the substudy will be monitored such that approximately equal proportions of subjects with STEMI, and NSTEMI will be recruited.

6.7. Genetic Research

Information regarding genetic research is included in [Appendix 4](#)

6.8. Pharmacokinetics

Blood samples for PK analysis of losmapimod will be collected at the time points indicated in [Table 3](#) and as detailed below from approximately 3850 subjects (~1925 subjects on active treatment) in Part B. The timing of PK samples may be altered and/or PK samples may be obtained at additional time points to ensure thorough PK monitoring. Deviations from the defined PK sampling scheme will not be considered protocol deviations.

- *In-hospital period:* During the in-hospital period PK samples should be drawn following the second and third dose. Following the second dose, samples should be collected within the following windows: 6–12 hours post dose (trough sample).

Following the third dose, samples should be collect within the following windows: 1–2 hours post-dose and 3–4 hours post dose. The exact time the PK samples are drawn and the exact time all doses are administered during the in-hospital period should be recorded in the source documents and entered into the CRF.

- *Week 4:* A blood sample should be drawn just prior to dosing of IP on the day of the Week 4 visit. The exact dosing times of IP on the day of each visit and on the day prior to each visit should be recorded in the source documents and entered into the CRF. For the doses prior to the visit, subjects should return a card on which the subject records this dosing information.

Details of the PK blood sample collection (included volume to be collected), processing, storage, and shipping procedures are provided in the laboratory manual.

7. DATA MANAGEMENT

For this study, subject data will be entered into a GSK-defined eCRF, transmitted electronically to GSK or designee and combined with data provided from other sources in a validated data system.

Management of clinical data will be performed in accordance with applicable GSK standards and data cleaning procedures to ensure the integrity of the data, e.g., removing errors and inconsistencies in the data. Adverse events and concomitant medications terms will be coded using the Medical Dictionary for Regulatory Activities (MedDRA) and an internal validated medication dictionary, GSKDrug. An appropriate medical dictionary that covers all approved drugs in studies where Japan is participating will be referenced. eCRFs (including queries and audit trails) will be retained by GSK, and copies will be sent to the investigator to maintain as the investigator copy. In all cases, subject initials will not be collected or transmitted to GSK according to GSK policy.

8. DATA ANALYSIS AND STATISTICAL CONSIDERATIONS

This study is an operationally seamless design to be conducted in two stages (Part A and Part B) as described in Section 3.1. The primary inference for efficacy will be based on an assessment of the data from the main event driven cohort (Part B).

The primary inference for safety will be based on an assessment of the combined safety database from both cohorts (Part A + Part B).

In summary, the primary analysis of MACE at 12 weeks will be based on a stratified log-rank test with a stratified Cox-regression model used to estimate the hazard-ratio and its 95% confidence interval (both analyses stratified by NSTEMI/STEMI). Key secondary endpoints will be assessed using the same methods as the primary endpoint, with overall significance controlled for multiplicity at the 5% level. With 1,400 primary events the study would have 90% power for statistical significance at $p < 0.05$ based on a true benefit of 16% relative risk reduction. Further details are described below.

8.1. Hypotheses

The primary efficacy analysis (Part B) will assess the time to first occurrence (in days) of MACE from randomization up to and including Week 12 (Day 84).

The primary objective of the study is to assess superiority of treatment with losmapimod relative to placebo on top of a background of standard care.

The primary analysis will assess superiority of treatment with losmapimod relative to placebo on time to first occurrence of MACE through 12 weeks of therapy. Statistical significance will be assessed at the two-sided 5% level by a log-rank test, stratified by NSTEMI/STEMI status at baseline.

A two-sided 5% significance level will be used to test the following hypotheses:

- Null hypothesis: The hazard functions for MACE are the same for both losmapimod and placebo treated subjects
- Alternative hypothesis: The hazard functions differ between losmapimod and placebo treated subjects

A stratified Cox-regression model, stratified by NSTEMI/STEMI, will be used to estimate the hazard-ratio and its 95% confidence interval. A hazard ratio < 1 will correspond to a benefit of losmapimod relative to placebo.

The primary efficacy endpoint (MACE) will be tested first and if the null hypothesis is rejected, the principal secondary endpoint (CV death or MI) will be tested, before proceeding to other secondary endpoints as part of a serial gate keeping procedure, the details of which are addressed in the RAP. If either the primary or principal secondary null hypotheses fail to be rejected, the other secondary endpoints will be tested in an exploratory manner.

8.2. Study Design Considerations

The study is designed to assess superiority of treatment with losmapimod relative to placebo on top of a background of standard care. It will be a randomized, placebo-controlled, double-blind, parallel group, international, multicenter, two-stage design.

In total, approximately 25,500 ACS subjects will be recruited, comprising 3,500 subjects in a leading cohort (Part A) used to provide an initial assessment of safety and exploratory efficacy with approximately 200 MACE (defined as CV death, MI, or severe recurrent ischemia requiring urgent coronary artery revascularization); followed by a main cohort of approximately 22,000 subjects (event target of 1,400 MACE and 1,000–1,200 CV death or MI).

8.2.1. Sample Size Assumptions

Assessment of MACE Efficacy from Part A

The pivotal and powered assessment of efficacy will be provided by Part B of the study, with Part A providing an exploratory assessment to support continuation to Part B.

Whilst an exploratory cohort could not be well powered for formal assessment of efficacy, the precision with which the MACE effect size can be estimated from Part A has been considered. For example, with approximately 200 subjects anticipated to experience at least one MACE event, an observed relative risk of 0.8 would have an associated 95% confidence interval of approximately 0.61 to 1.05, whilst an observed relative risk of 1.0 would have a 95% confidence interval of approximately 0.76 to 1.31. Given the limitations on precision that would be expected in an exploratory context, the decision to progress to Part B will be multifaceted.

Assessment of Efficacy in Part B

The size of Part B has been determined based on an event target of 1,400 adjudicated primary endpoint events. It is anticipated that approximately 22,000 subjects will be

recruited to achieve this event target. The primary endpoint event target is expected to include 1,000–1,200 CV death or MI events. These estimates are based on a projected 12 week MACE event rate of ~7% for the placebo group, and an assumed 20% relative risk reduction for subjects in the losmapimod group. Within the composite of MACE, it is estimated that the incidence of CV death/MI will be 5% to 6% and that SRI-UR will be 1% to 2%.

The principal efficacy evaluation will occur up to Week 12 with additional evaluations of efficacy at Weeks 4 and Week 24.

A total of 1,400 adjudicated primary MACE events (CV death, MI, and SRI-UR) occurring within the principal study time point of 12 weeks will provide approximately 90% power to detect a 16% reduction in risk (hazard ratio=0.84) at a 5% significance level. At the 5% significance level, the minimum detectable effect (i.e., the smallest effect to give a significant p-value) is approximately 10%.

The principal secondary endpoint of CV death/MI will be tested provided the primary endpoint is statistically significant at the 5% level. For the principal secondary endpoint of CV Death or MI: a minimum of 1,000 adjudicated events will provide approximately 90% power to detect an 18.5% reduction in risk (hazard ratio=0.815) and close to 80% power to detect a 15% reduction in risk at a 5% significance level. At the 5% significance level, the minimum detectable effect (i.e., the smallest effect to give a significant p-value) is approximately 12%.

The anticipated placebo MACE event rate (~7%) is estimated from the ticagrelor treatment group of the PLATO study using the individual Kaplan-Meier cumulative event rate estimate from the NSTEMI (7.1%) and STEMI (6.0%), taking into account a 20% reduction in events as a consequence of the recent changes to the universal definition of MI and the use of SRI-UR as a replacement for stroke.

The aggregate event-rate data will be periodically reviewed by the Executive Committee and sponsor. Should emerging data diverge significantly from protocol assumptions the total sample size to achieve the event target for Part B may be adjusted if deemed appropriate.

Recruitment may be closed prior to 1400 events if the sample size for part B is anticipated to exceed 24,000 subjects.

Assessment of Safety in Parts A & B1

All 25,500 subjects estimated to enroll in the trial would contribute to a robust overall safety database of clinical adverse events, including liver events.

In addition, the totality of available safety data from Part A (N=3,500) will be evaluated prior to starting Part B, and an additional formal evaluation of safety will be conducted by the IDMC once Part B has enrolled approximately 3,500 subjects (completion of Part B1), to support a combined analysis of 7,000 subjects' safety data. After this point, if considered appropriate by the IDMC, the time and events schedule for data collection will be revised (Section 6). As noted, such decisions will be made based on the totality of

the data, but for illustrative purposes, power and detectable effect with respect to aspects of safety analysis has been considered.

Based on an anticipated placebo incidence of ALT $\geq 3 \times$ ULN of 2.5%, if there is a true underlying absolute risk increase with losmapimod of 1.2% (approximate relative increase of 1.5-fold), then with 7,000 patients at the end of Part B1 there is 83% power to observe a significant difference. The smallest observed risk difference that would reach statistical significance (i.e., the minimal detectable effect) is ~0.8% (approximately 30% increase in relative-risk increase terms) at a 2-sided 5% level.

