3.1.4. Treatment Phase

The Treatment Phase begins at randomization.

In-hospital Period

In both Parts A and B, subjects who are eligible for the study will be randomized 1:1 to receive oral losmapimod 7.5 mg BID or matching placebo (referred to as investigational product [IP]) for 12 weeks (+2 weeks). Separate randomization schedules will be generated for Part A and Part B.

It is anticipated that the majority of the total study population will undergo coronary revascularization (i.e., percutaneous coronary intervention [PCI] or coronary artery bypass grafting [CABG]) for the qualifying event, consistent with current therapeutic guidelines for high risk ACS patients. Invasive evaluation is not mandated to qualify for the study, but if a subject is to undergo coronary revascularization for the qualifying

event, randomization and administration of the first dose of IP must occur prior to revascularization. If a subject has undergone coronary revascularization for the qualifying event prior to randomization, he/she is no longer eligible for the trial, even if additional PCI procedures are planned.

Analogously, for subjects with STEMI undergoing fibrinolysis, subjects must be randomized and administered the first dose of IP prior to administering any fibrinolytic treatment. If a subject has received a fibrinolytic for the qualifying MI prior to randomization, he/she is no longer eligible for the trial. It is anticipated that most subjects undergoing fibrinolysis will be referred for coronary angiography, ideally between 3 to 24 hours after fibrinolytic administration.

IP should be administered within 2 hours after randomization, and prior to starting any coronary revascularization procedure or fibrinolytic administration for the qualifying event.

Subjects will be followed throughout their hospitalization with a pre-discharge assessment for potential endpoints and adverse events (Table 1). Subjects who are transferred from the enrolling study center to another hospital for continued care should continue IP and study procedures according to the protocol. For subjects transferred to a hospital not participating in the study, study procedures should be conducted, whenever possible.

After Hospital Discharge

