8.3.3. Treatment Comparisons

8.3.3.1. Primary Comparisons of Interest

The primary comparison of interest is the comparison of the survival functions of adjudicated MACE followed by CV death or MI in a closed testing procedure for losmapimod vs. placebo (using a stratified log-rank test) in Part B. The ITT population will be utilized for this comparison. The comparison will be performed for events occurring within the period from randomization to Week 12 at the two-sided 5% significance level.

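### Power for CV death/MI at a 15% risk reduction is given as close to 80% with 1,000 events; the protocol's own method gives 73%

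*Protocol*

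**What the plan says.** Section 8.2.1 of the protocol sizes Part B by 1,400 adjudicated primary events. Of the CV death/MI events within that total it says: "The primary endpoint event target is expected to include 1,000–1,200 CV death or MI events".

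For the principal secondary endpoint it then states that "a minimum of 1,000 adjudicated events will provide approximately 90% power to detect an 18.5% reduction in risk (hazard ratio=0.815") and, in the same sentence and for the same event count, "close to 80% power to detect a 15% reduction in risk at a 5% significance level". It adds that the smallest observed effect reaching significance is about 12%.

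The test is set out in Section 8.3.3.1. It is a stratified log-rank test in Part B, and "The comparison will be performed for events occurring within the period from randomization to Week 12 at the two-sided 5% significance level". Section 3.1.4 gives 1:1 allocation. Under Section 8.1, CV death/MI is tested only if the primary null hypothesis is rejected. If either of these two tests fails, the remaining secondary endpoints are exploratory.

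**The concern.** Both power figures rest on one event count, one significance level and one test, so they should be consistent with each other. They are not. With the number of events fixed, moving from a hazard ratio of 0.815 to 0.85 lowers power from about 90% to well below 80%.

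The figure describes the first gate after the primary endpoint, behind which every other confirmatory secondary test sits. A 15% reduction is a realistic scenario, since the primary endpoint's own 90% power is quoted for a 16% reduction. The low end of the event range also matters in practice: Section 8.2.1 allows recruitment to close before 1,400 primary events if Part B is expected to exceed 24,000 subjects. Anyone weighing that option would read the chance of missing a 15% effect on CV death/MI as about one in five.

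**Working it through.** **Inputs**

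- Events: 1,000 (stated minimum), with an expected range of 1,000 to 1,200 (Section 8.2.1).
- Effect: a 15% reduction, read as HR 0.85. The protocol does not print this hazard ratio, but it pairs 18.5% with 0.815 and 16% with 0.84 in the same section.
- Test: log-rank, two-sided 5% (Section 8.3.3.1), so the critical value is 1.96.
- Allocation: 1:1 (Section 3.1.4).

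**Formulas** (Schoenfeld approximation, D events, equal allocation)

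- Power = Φ(√(D/4) × |ln HR| − 1.96)
- Smallest significant effect = 1 − exp(−2 × 1.96/√D)
- Events for 80% power = 4 × (1.96 + 0.8416)² / (ln HR)²

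**Step 1: reproduce the figures around the disputed one**

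| Quantity | Protocol | Computed |
|---|---|---|
| Power, 1,400 events, HR 0.84 | about 90% | 90.4% |
| Power, 1,000 events, HR 0.815 | about 90% | 89.9% |
| Smallest significant effect, 1,400 events | about 10% | 9.9% |
| Smallest significant effect, 1,000 events | about 12% | 11.7% |

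All four agree, so the formula matches the protocol's figures.

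**Step 2: the disputed figure**

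1,000 events, HR 0.85: √250 × 0.1625 − 1.96 = 15.81 × 0.1625 − 1.96 = 0.610, and Φ(0.610) = **72.9%**.

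**Step 3: what would give 80%**

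- Events needed at HR 0.85: 4 × 2.8016² / 0.1625² ≈ 1,189.
- Power at HR 0.85: 72.9% with 1,000 events, 76.9% with 1,100, 80.4% with 1,200.
- Hazard ratio needed with 1,000 events: exp(−2 × 2.8016/√1000) = 0.838, a 16.2% reduction. HR 0.84 gives 15.81 × 0.1744 − 1.96 = 0.797, or 78.7%.

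**Step 4: other methods at 1,000 events and a 15% reduction**

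| Method | Power |
|---|---|
| Freedman, two-sided 5% | 72.7% |
| Schoenfeld with allocation set to the expected event split | 72.6% |
| Two proportions, 11,000 per arm, risk ratio 0.85 | 74.7% |
| Schoenfeld, one-sided 5% | 82.2% |

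No two-sided method exceeds 75%. The one-sided result conflicts with the stated two-sided test, and it would also turn the companion figure for HR 0.815 into 94.4% instead of 90%.

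**The case against.** The best counter-argument accepts the arithmetic and disputes its weight.

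- **The figure sets nothing in the design.** Part B is sized by 1,400 primary events, and the CV death/MI count is only what that total is expected to contain. The primary power, the lead power figure for CV death/MI and both smallest significant effects are correct. This stands: correcting the clause changes no sample size, event target, test or decision rule.
- **The wording is hedged.** The text says close to 80% and speaks of a minimum, and 80.4% is reached at 1,200 events. This helps only in part. The sentence attaches the figure to 1,000 events, where the gap is about 7 points, while the neighbouring power figures agree to within half a point.
- **A 15% effect is weaker than planned.** Section 8.2.1 assumes a 20% reduction in MACE when projecting event numbers. If that also held for CV death/MI, 1,000 events would give 15.81 × 0.2231 − 1.96 = 1.568, or about 94% power. That is fair context, but the protocol chose to report the 15% case and the number it gives is wrong. Section 8.3.3.2 does warn in general terms that secondary analyses may have less power, but that does not correct a specific figure.
- **The cause is unknown.** The figure may have been worked out near 1,200 events, or 15% may have been written for 16%, since HR 0.84 at 1,000 events gives 78.7%. The protocol does not say which, and the finding does not depend on it.

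**Conclusion.** The statement is wrong as written. At the minimum of 1,000 events, power to detect a 15% reduction in CV death/MI is about 73%, roughly 7 percentage points below the printed figure. The type II error is about 27% instead of about 20%, about one-third higher. Reaching 80% takes about 1,189 events, 19% more than the stated minimum.

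This rests on reading a 15% reduction as HR 0.85, on proportional hazards, and on the two-sided 5% log-rank test with 1:1 allocation that the protocol specifies. It is marginal power for the CV death/MI test. If HR 0.85 held for both endpoints, with 1,400 and 1,000 events and a correlation of √(1000/1400) between the test statistics, the chance of passing both gates would be about 71%. The protocol states neither of those two assumptions, so that number is illustrative.

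The error is confined to the principal secondary endpoint. The primary endpoint's power, the type I error and the size of the trial are untouched.

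**What to change.** In Section 8.2.1, replace the second half of the sentence on CV death/MI power in one of two ways:

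- *about 73% power for a 15% reduction (hazard ratio 0.85) with 1,000 events, rising to about 80% with 1,200*; or
- keep the 80% figure and attach it to the effect it fits: *close to 80% power for a 16% reduction (hazard ratio 0.84) with 1,000 events*. The computed value is 78.7%; exactly 80% corresponds to a hazard ratio of 0.838.

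The first is preferable because it keeps the 15% scenario and shows how power changes over the expected event range. Adding the chance of passing both gates is optional; if it is given, its assumptions should be stated with it.

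The cost is one clause and a slightly less favourable figure. No other part of the design needs to change.

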8.2.2. Sample Size Sensitivity

If the placebo event rate for MACE at 12 weeks in Part B is lower than the assumed 7%, the resulting impact on the number of MACE events / the number of subjects to achieve 1,400 MACE events in the main cohort is shown in Table 4 assuming a 20% treatment effect (HR=0.8).

Table 4 MACE Sensitivity for Varying Placebo Event Rates

Placebo Event Rate (at 3 months)	Number of Subjects to achieve 1,400 MACE [†]	Number of MACE (from 22,000 subjects) [†]
7.1%	21,900	1,400
7.0%	22,100	1,380
6.8%	22,800	1,340
6.6%	23,500	1,300
6.4%	24,200	1,270
6.2%	25,000	1,230
6.0%	25,900	1,190

[†] Subject numbers are rounded to the nearest 100. Event numbers are rounded to the nearest 10 events.

8.2.3. Sample Size Re-estimation

The aggregate event-rate data will be periodically reviewed by the Executive Committee and the sponsor. The study has an event-driven design. Should emerging data diverge significantly from protocol assumptions, the total sample size will be adjusted, within the bounds of feasibility, to achieve the event target for Part B.

8.2.4. Decision-making Criteria for Part A

The assessment of safety and efficacy in subjects with ACS is multi-faceted and hence there is no single decision algorithm for initiating Part B under all possible scenarios. However, a decision to proceed to Part B can only be made with endorsement with respect to safety from the IDMC. With respect to efficacy, a risk reduction in the incidence of the primary endpoint (the composite of adjudicated MACE), accompanied by supporting secondary endpoint data, may be considered an indication to begin enrollment in Part B, provided the IDMC has not identified any meaningful safety concerns.

8.3. Data Analysis Considerations

8.3.1. Analysis Populations

The primary population for all analyses of MACE, secondary time-to-event outcomes and other efficacy assessments will be the All Randomized (ITT) Population. Subjects will be analysed according to the treatment to which they were randomized.

The primary population for safety in the study will be based on all randomized subjects from Part A and Part B combined, who have received at least one dose of IP. Subjects will be analysed according to the treatment which they actually received.

Any further populations to be used for the assessment of PK, biomarker, genetic and health economic outcomes data will be defined in the RAP.

